7.7 Heart Team meeting structure & organization

The Heart Team should involve an interventional cardiologist, cardiac surgeon, radiologist (experienced coronary CT reader) and study coordinator.

It is recommended to execute the different levels of decision making during *one* Heart Team session. In other words, one should start the Heart Team meeting only when all information is available and accessible, i.e. anatomic SYNTAX Score by Angio and CT (by site and by Core Lab), SYNTAX Score II and functional anatomy (FFR_{CT}). Randomization is performed via the eCRF module. The *Heart Teams* are randomized to one of two groups (1:1) to either 'Angio-first algorithm' or 'MSCT-first' algorithm.

Angio first algorithm: Screen the patients first by means of conventional invasive angiography (i.e. anatomical SYNTAX Score [visual] and SYNTAX Score II) and record the first decision making on choice of revascularization (PCI or CABG), planning of revascularization measures (# of stents / # of grafts), and localization of diseased segments needing revascularization in the

eCRF. As an external reference, the independent Core Lab also provides anatomical SYNTAX Score for consultation. After the first decision making recording, the additional information of CT and the functional severity assessment is disclosed and the Heart Team completes the second decision based on information derived from both modalities.

CT first algorithm: Screen the patients first by means of non-invasive CT (i.e. anatomic SYNTAX Score [visual by experienced coronary CT reader/radiologist] and SYNTAX Score II and record the first decision making on choice of revascularization (PCI or CABG), planning of revascularization measures (# of stents / # of grafts), and localization of diseased segments needing revascularization in the eCRF. The radiologist of the Heart Team provides anatomical SYNTAX Score on MSCT, which is primarily used for decision making. As an external reference, the independent Core Lab also provides anatomical SYNTAX Score on MSCT for consultation.

After the first decision making recording the functional anatomy (FFR_{CT}) is disclosed to the Heart Team. The Heart Team recalculates the SYNTAX Score (I and II) by subtracting the (SYNTAX Score) points of non-flow limiting lesions (>0.80) and makes the second decision (incremental value FFR_{CT}). Next, the additional information of conventional angiography is disclosed and the Heart Team makes the third decision based on information derived from both modalities.

For the first, second and third decision making, the Heart Team records following items in the eCRF (as well as for the final/actual treatment):

- a. choice of revascularization mode: PCI/CABG;
- b. number of diseased vessels/diseased lesions;
- c. diseased segment numbers

Final decision of treatment recommendation will be left at the discretion of the Heart Team after formal dialogue with the patient and provision of the prognostic information. The Heart Team may overrule the treatment recommendation made by the online calculator whenever the Heart

Team identifies significant additional clinical risks which are not addressed in the SYNTAX Score II. Reasons for undertaking this should be clearly documented in the eCRF

Note: the Heart Team must co-sign and document in the eCRF (including date and time) each decision-making following the assigned algorithm prior to the unblinding with the complementary information (either Angio or MSCT, or functional anatomy). *Note*: the physicians involved in the initial angiography/catherization or MSCT acquisition are not 'blind' for both imaging modalities and as a consequence cannot be part of the study Heart Team (randomisation).

7.8 Data-flow

The data-flow, the export of images, and the access to Core Lab SYNTAX Scores and FFR_{CT} will be described in a separate manual.

8 STATISTICAL DESIGN AND ANALYSIS

8.1 Introduction

The SYNTAX III REVOLUTION Trial is a multicenter, all-comers trial aiming at randomizing two Heart Teams. Each patient will be assessed by two Heart Teams, the first Heart Team will perform a clinical decision based on SYNTAX Score II analysis with angiographic information (Angio first), the second Heart Team will perform a clinical decision based on SYNTAX Score II analysis with MSCT information (CT first). For both strategies the Heart Team will lead to one of three treatment recommendations:

CABG-only.

1. *CABG-only*. Patient should be treated by CABG due to high 4-year mortality of PCI according to therapeutic recommendation of SYNTAX Score II.

PCI-only/ Equipoise.

1. *Equipoise*. Patient could be treated by either CABG or PCI, considering that the 4-year mortality prediction is similar between PCI and CABG.

2. *PCI-only*. Patient should be treated by PCI due to high 4-year mortality of CABG according to therapeutic recommendation of SYNTAX Score II.

8.2 Intent-To-Treat population

The 'Intend-to-Treat' population consists of all patients having a GE Revolution CT scan performed and for whom the Heart Team is randomly assigned to an "Angio-First" or a "CT-First" decision algorithm.

8.3 Sample size

The SYNTAX III REVOLUTION Trial is powered to show substantial inter-rater agreement between the Heart Team recommendation ("CABG only" or "PCI only/Equipoise") based on the *Angio first* algorithm and the Heart Team recommendation ("CABG only" or "PCI only/Equipoise") based on the *CT first* algorithm.

The inter-rater agreement will be assessed by Cohen's Kappa, on revascularization strategy of two Heart Teams using an "Angio-first" algorithm (based on invasive SYNTAX Score II) or a "CT-first" algorithm (based on non-invasive SYNTAX Score II, without FFRCT).

A Kappa of 0.60 to 0.80 is considered to show substantial agreement.¹ We expect the two Heart Team decisions to reach an almost perfect agreement (Kappa=0.80).¹

Given these assumptions:

- Both the *Angio first* diagnostic algorithm and the *CT first* diagnostic algorithm will result in the "CABG-Only" treatment decision for 30% of the patients,
- An almost perfect agreement (Kappa=0.80),
- 90% power to show at least substantial agreement (Kappa>=0.60)
- and a 5% two-sided alpha

a sample size of 200 patients will be sufficient for achieving 90% power to reach a positive trial.² Assuming an attrition rate of maximum 10%, 223 patients will be included in the study.

8.4 Intend-to-Treat Analysis

All analyses will be performed for the Intend-to-Treat population only.

8.5 Analysis of the Primary Endpoint

The inter-rater agreement will be assessed by Cohen's Kappa, on revascularization strategy of two Heart Teams using an "Angio-first" algorithm (based on invasive SYNTAX Score II) or a "CT-first" algorithm (based on non-invasive SYNTAX Score II, without FFR_{CT}). A 95% two-sided confidence interval will be calculated for Kappa, using the asymptotic variance of the Kappa coefficient and applying the standard normal distribution.⁷²

If the lower limit of this confidence interval is 0.6 or higher the trial is considered to be positive. If the lower limit of this confidence interval is less than 0.6 the trial is considered to be negative.

8.6 Analysis of the Secondary Endpoints

No formal testing will take place for the secondary endpoints.

Secondary Endpoints measuring Inter-Rater agreement

Secondary Endpoints that measure inter-rater agreement are for the following situations:

- A comparison between the treatment recommendation between two diagnostic algorithms (*CT only* versus *Angio only*) at the same decision moment
- A comparison between the treatment recommendation for the same diagnostic algorithm (e.g. *CT only*) but for different levels of available information

Agreement is reached when both algorithms recommend "CABG only" or both algorithms recommend "PCI only/Equipoise".

In both cases the inter-rater agreement will be measured by:

- 2*2 tables showing the treatment recommendations ("CABG only"/"PCI only/Equipoise") for the compared situations.
- The percentage of patients with agreement between the algorithms and its 95% two-sided Confidence Interval (using the Clopper-Pearsons (Exact) approach).
- The inter-rater agreement as measured by Cohen's Kappa and its 95% two-sided Confidence Interval for Kappa using the asymptotic variance of the Kappa coefficient and applying the standard normal distribution.⁷²

Additionally these endpoints measuring agreement will be reported.

- Concordance in SYNTAX Score(s) between and within strategies, measured as the difference in SYNTAX Score(s) points.
- Agreement in coronary stenosis segments to be revascularized between and within strategies (using AHA 16 segment model).^{73,74}
- An ad-hoc defined composite endpoint combining

-Concordance in SYNTAX Score(s)

-Agreement in coronary stenosis segments to be revascularized

-Agreement between treatment recommendation.

Continuous secondary endpoints

- Anatomical SYNTAX Score calculation based on non-invasive GE Revolution CT (visual by Heart Team involving a radiologist)
- Anatomical SYNTAX Score calculation based on non-invasive GE Revolution CT (visual by Core Lab)
- Anatomical SYNTAX Score calculation based on invasive Angiography (visual by Heart Team)
- Anatomical SYNTAX Score calculation based on invasive Angiography (visual by Core Lab)
- Functional SYNTAX Score by non-invasive FFR_{CT} (Heartflow)
- SYNTAX Score II derived from either conventional angiography (CA) or non-invasive angiography (CTA) by Heart Team

8.7 Descriptive statistical methodology

All statistical analyses will be done using the SAS System software, version 9.3 or above (SAS Institute Inc., SAS Campus Drive, Cary, North Carolina 27513, USA. All rights reserved).

Inter-rater agreement will be assessed by Cohen's Kappa. A 95% two-sided confidence interval will be calculated, using the asymptotic variance of the Kappa coefficient and applying the standard normal distribution.⁷²

Continuous endpoints will be summarized by their mean, standard deviation, number of observations, median, minimum, maximum and interquartile range. The variable means are evaluated by a paired t-test, the difference between treatments and its 95% confidence interval will be reported.

Categorical variables are summarized by frequencies and percentages. Baseline Characteristics

Demographics, medical history and other clinically relevant baseline variables will be tabulated. In principal patient oriented percentages refer to the proportion of patients with the characteristic present.

9 QUALITY CONTROL AND QUALITY ASSURANCE

9.1 Compliance to Standards and Regulations

The protocol, informed consent form and other study-related documents will be submitted to the Ethics Committee (EC) / Institutional Review Board (IRB). The study will be performed in accordance with the Declaration of Helsinki and Good Clinical Practices (GCP).

The trial will only start at a clinical site after written approval of the study has been obtained from the appropriate national EC/IRB.

9.2 Quality Assurance and Monitoring

Monitoring the clinical investigation at the study site is the responsibility of the monitoring organisation through trained and qualified Clinical Research Associates (CRAs).

The study Sponsor, or designee, will monitor the study to ensure proper conduct and progress of the study including adequate protection of human subjects and the integrity of the clinical study data. It may include initiation and close-out visits. This will also include routine, periodic visits to study sites to confirm reported results are consistent with source documentation, appropriate subject enrollment, compliance with all applicable laws and regulations, and compliance with the protocol. Remote monitoring may also occur. The frequency of monitoring visits will be based upon enrollment, data integrity, and site compliance. A Monitoring Plan will be written for the study and will be kept separate from the protocol. Each study site will allow monitoring activities to be conducted at their site, including visits by the study Sponsor and/or their designee. Therefore, access to the patients' files must be allowed as per the informed consent at the Investigator's site.

9.3 Quality Assurance and Data management

The data collection will be performed through an electronic CRF (eCRF). The investigator or an authorised member of the investigational team must sign all completed eCRFs by using an

electronic signature (a password will be provided by the data management centre at the start of the study).

Clinical data management will be performed in accordance with data cleaning procedures. This is applicable for data recorded in the eCRF as well as for data from other sources (e.g. angiographies, CTs, etc.). Appropriate computer edit programs will be run to verify the accuracy of the database. The investigator will be queried on incomplete, inconsistent or missing data.

9.4 On-site Audits

To ensure compliance with GCP and regulatory requirements, a member of the Sponsor's (or a designated CRO's) quality assurance unit, may arrange to conduct an audit to assess the performance of the study at the study site and of the study documents originating there. The investigator agrees to cooperate with the Sponsor and/or its designee in the conduct of these audits and provide access to medical records and other relevant documentation, as required. The investigator/institution will be informed of the audit outcome.

Regulatory authorities worldwide may inspect the investigator during and after the study. The investigator should contact the sponsor immediately if this occurs, and must cooperate with the regulatory authority inspections as required.

10 ORGANISATION

10.1 Sponsor

In this investigator-initiated trial, the European Cardiovascular Research Institute (ECRI) will act as Sponsor (ECRI-Trials B.V., [name],). The Sponsor's responsibilities are described in chapter 14.

10.2 Steering Committee

The Steering Committee is responsible of the overall management of the study. The Steering Committee is comprised of a Chairman, PIs, co-PIs, and ECRI. Their names, roles and responsibilities are described in a separate Steering Committee Charter.

10.3 Clinical Event Committee (CEC)

Not applicable.

10.4 Data Safety Monitoring Board (DSMB)

Not applicable.

10.5 Data Management

Data management will be conducted by the Clinical Research Organisation (CRO) Cardialysis (Cardialysis B.V., [name]).

10.6 Site Management and Monitoring

The CRO Cardialysis (Cardialysis B.V., [name]) will be responsible for site management and monitoring.

10.7 Safety Reporting

For the study patient, this study is ended after the MSCT acquisition has been performed. The clinical treatment decision-making and patient treatment is up to investigators' discretion and no follow-up investigation is implemented. Serious Adverse Events occurring between the moment the subject gave Informed Consent until the MSCT acquisition has been performed must be documented in the eCRF if considered related to study procedures within 24 hours. The investigator must inform Ethical Committee and manufacturers conform local practice.

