	 The sources of information are: Invasive Angiography Non-invasive GE Revolution CT Functional anatomy by non-invasive FFR_{CT} (Heartflow) The results to be compared are: Agreement on treatment recommendation Agreement on treatment recommendation between different levels of available information Agreement in coronary stenosis segments to be revascularized Anatomical SYNTAX Score and the resulting SYNTAX Score II 		
Number of Patients	Approximately 223 patients in total.		
Investigational Sites	Approximately 5-10 sites in Europe.		
Follow-up	No follow-up assessment/visits. Study end after final Heart Team clinical decision making.		
Primary Endpoint	Inter-rater agreement, as assessed by Cohen's Kappa, on revascularization strategy of two Heart Teams using an "Angio-first" algorithm (based on invasive SYNTAX Score II) or a "CT-first" algorithm (based on non-invasive SYNTAX Score II, without FFR_{CT}).		
Secondary Endpoints	 Level of agreement in the decision making strategy based on CT only without functional assessment and the decision making strategy based on CT with functional assessment ("CT first" algorithm group). Level of agreement in the decision making strategy based on CT only (with functional assessment) and the decision making strategy based on CT with functional assessment and conventional angiography ("CT first" algorithm group). Level of agreement in the decision making strategy based on conventional angiography only and the decision making strategy based on conventional angiography only and the decision making strategy based on CT with functional assessment and conventional angiography ("Angio first" algorithm group). Inter-rater agreement on revascularization strategy (based on conventional angiography and CT with functional assessment) of two Heart Teams using an "Angio-first" algorithm or a "CT-first" algorithm. Anatomical SYNTAX Score calculation based on non-invasive GE Revolution CT (visual by Heart Team involving an experienced coronary CT reader) and the resulting SYNTAX Score II. 		

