4 STUDY DESIGN

The SYNTAX III REVOLUTION Trial is a multicenter, all-comers* trial aiming at randomizing two Heart Teams who would have to make a decision between surgical or percutaneous treatment according to either an invasive conventional angiography or a non-invasive multislice CT angiography assessment in approximately 223 patients in approximately 5-10 interventional cardiology centers in Europe. *Patients with de novo 3-vessel disease or left-main disease (isolated or associated with 1, 2 or 3 vessel disease) will be eligible.

For each given patient the Heart Team is randomly assigned to an "Angio-First" or a "CT-First" decision algorithm. There will be two (2) independent Heart Teams per hospital, and each patient will be assessed by both teams. The concordance or discordance of decision makings based on

Protocol ECRI-004 Version 1.0 Page 24 of 66

either conventional angiography (Angio first algorithm) or MSCT angiography (CT first algorithm) will be assessed and constitute the primary endpoint of the trial. In addition, the incremental value of FFR_{CT} in the decision making of the Heart Team arm allocated primarily to the assessment of the MSCT (CT first algorithm) will be a secondary endpoint.

Patient study participation will end after final Heart Team treatment decision. The ultimate choice of treatment is up to the discretion of the physician/Heart Team.

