7.2 Patient Information and Informed Consent

If the eligibility of the patient is confirmed according to inclusion and exclusion criteria, patients must be consented prior to undergoing any study-specific procedures. Once the patient's general eligibility for the study is met, the background of the proposed study and the benefits and risks of the study must be explained to the patient prior to obtaining informed consent. Only those patients who sign the Ethics Committee approved informed consent form prior to any study-specific procedures (MSCT scanning with GE 256-slice REVOLUTION scanner) are candidates for actual enrolment in the study. Failure to provide written informed consent renders the patient ineligible for the study.

The investigator and/or designee must also clearly document the process of obtaining informed consent in the subject's source documents. The voluntary process of obtaining informed consent confirms the subject's willingness to participate in the study. It is the investigator's responsibility to ensure that the informed consent process is performed in accordance with ISO14155, EC requirements and country specific regulations.

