7.4 MSCT

Prior to the Heart Team randomization, a MSCT scan must be obtained utilizing the 256-slice GE Revolution* CT scanner. Refer to Appendix IV for MSCT acquisition guidelines.

*A patient may be diagnosed/enrolled based on previously performed MSCT (but solely, if that CT was performed with the 256-slice GE Revolution CT scanner and within 1 month prior to patient enrolment.

 FFR_{CT} will be used in the incremental process of Heart Team discussion (= secondary endpoint). The MSCT-derived FFR (FFR_{CT}) will only be disclosed after the first decision making has been concluded.

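### Section 10.7 ends both the study and the SAE onset window at the CT scan, in conflict with Sections 4 and 13.6, so a scan-related SAE that begins afterwards need not be documented under it

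*Combined protocol and SAP*

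**What the plan says.** Three parts of the combined protocol and SAP bear on when a patient's participation ends and which SAEs must be recorded.

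- **Section 10.7 (Safety Reporting)** ends the study at the scan: "For the study patient, this study is ended after the MSCT acquisition has been performed". It then sets the collection rule: "Serious Adverse Events occurring between the moment the subject gave Informed Consent until the MSCT acquisition has been performed must be documented in the eCRF", provided the event is judged related to study procedures. The same section says that "no follow-up investigation is implemented".
- **Section 4 (Study Design)** sets a later end: "Patient study participation will end after final Heart Team treatment decision". The study design row of the synopsis says the same, and its follow-up row agrees: "Study end after final Heart Team clinical decision making".
- **Section 13.6 (Reporting Requirements)** has a table asking sites to enter study-procedure-related SAEs in the eCRF within 24 hours of learning of them. It sets no limit on when the event began.

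The order of events is fixed by Section 7.4 ("Prior to the Heart Team randomization, a MSCT scan must be obtained") and by the schedule in Appendix I, which puts Heart Team preparation and the meeting after enrolment, scan and randomization. Section 7.2 requires consent "prior to any study-specific procedures (MSCT scanning with GE 256-slice REVOLUTION scanner") and names no other study-specific procedure. Section 7.4 also accepts an existing scan from the same scanner type if it was done "within 1 month prior to patient enrolment".

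**The concern.** The scan exposes the patient to iodinated contrast and, under Appendix IV, to nitroglycerin and in many cases a beta-blocker. Reactions to these can begin after the images have been taken. A collection rule that stops at acquisition stops just as that exposure is complete.

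Two things are at stake. First, a scan-related SAE with later onset need not be documented under the section that governs safety reporting. Second, sites reading Section 10.7 and sites reading Section 13.6 could apply different cut-offs, so the SAE listing would not mean the same thing at every site. No other mechanism is planned to pick such events up: there is no follow-up, and Sections 10.3 and 10.4 mark the event committee and the DSMB as not applicable.

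**Working it through.** No arithmetic applies. The check sets the passages side by side.

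**1. Timeline.** From Sections 7.2 and 7.4 and Appendix I, for a patient scanned within the study: consent, then MSCT acquisition, then Heart Team randomization, then Heart Team preparation, then the staged decisions, then the final decision.

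**2. Where each section places its limits.**

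| Source | End for the patient | Onset window for procedure-related SAEs |
|---|---|---|
| Section 10.7 | MSCT acquisition | Consent to MSCT acquisition |
| Section 4; synopsis | Final Heart Team decision | Not stated |
| Section 13.6 table | Not stated | No onset limit |
| Appendix III definitions | Not stated | Not stated |

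Acquisition and final decision are different moments, because randomization and all Heart Team work lie between them. That interval is inside the study under Section 4 and the synopsis, and outside both the study and the SAE window under Section 10.7. Its length is not stated.

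**3. Does the 24-hour phrase in Section 10.7 extend the window?** Its position in the sentence makes it possible to read it as a period after the procedure. Section 13.6 rules this out: there the 24 hours run from knowledge of the event and are a deadline for data entry. Even if the phrase qualified relatedness, the separate limit on onset at acquisition would remain.

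**4. Does the lack of outcome follow-up explain the cut-off?** No. Section 4 and the synopsis keep the patient in the study past the scan, and Sections 7.7 and 13.6 have the eCRF in use for the Heart Team decisions made after it.

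**5. Size.** Under Section 10.7 alone, the required window after acquisition is zero for any patient scanned within the study (223 are planned in total). No SAE rate is given, so an expected number of undocumented events cannot be derived.

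**6. Patients with an earlier scan.** The one-month allowance in Section 7.4 is counted back from enrolment, not from consent. Appendix I puts consent at screening and the scan at enrolment, so a scan before enrolment may fall on either side of consent. If it came before consent, it was not a study procedure within Section 7.2, and there was no study exposure to monitor. If it came after, Section 10.7 applies as to anyone else. The protocol does not say which is meant.

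**The case against.** The strongest reply is that the Section 13.6 table is what sites work from. It asks for procedure-related SAEs without an onset limit, so a site following it would enter a contrast reaction that began after the scan. This stands in part. A reader might infer from Section 10.7 that events after the scan are invisible to the trial, and the documents do not support that. What they support is that such events are not required under Section 10.7 and appear to be wanted under Section 13.6. That is a conflict of scope, and it leaves the rule to each site's reading.

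A second reply is that safety is neither an objective nor an endpoint, and Section 8 plans no safety analysis. That is correct and limits the consequence to reporting. It does not make the two sections consistent.

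Three stronger readings should also be set aside:

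- **Attrition.** A reader might infer that two end dates blur the 10% attrition allowance. They do not. Section 8.2 defines the analysis population by having had the scan and a randomized Heart Team assignment, with no reference to end of study. A patient lost before randomization is outside it, and one lost after is inside it, whichever end date is used.
- **Earlier scans.** A reader might infer a safety gap where the scan predates consent. Since such a scan would not be a study procedure, an empty window is expected there. Only a clarification is needed.
- **Cost.** A reader might assume that a longer window adds only a few days. The documents give no scan-to-decision interval, so no figure can be attached.

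**Conclusion.** The point holds as a contradiction in the current text with one practical consequence. Section 10.7 ends the study and the SAE window at acquisition, Section 4 and the synopsis end participation later, and Section 13.6 sets no onset limit. Followed as written, Section 10.7 does not require documentation of a scan-related SAE that begins after the scan.

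This conclusion rests on reading the onset limit in Section 10.7 literally and on the 24 hours being an entry deadline, as Section 13.6 indicates. The number of events affected is unknown. The primary kappa analysis, the 10% attrition assumption and the sample size of 200, or 223 with attrition, are unaffected. It is worth correcting because the rule concerns the trial's only named study-specific procedure and a wording change is enough.

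**What to change.** 1. Reconcile the synopsis (study design and follow-up rows), Section 4 and Section 10.7 so that they state one end of patient participation.
2. In Section 10.7, remove the onset limit at acquisition, so that procedure-related SAEs beginning after the scan are collected at least up to the stated end of participation. Give the Section 13.6 table the same scope.
3. Word the 24 hours in Section 10.7 as a reporting deadline counted from knowledge of the event, as in Section 13.6.
4. Add a sentence saying how Section 10.7 applies to patients enrolled on a previously performed MSCT, separating scans before consent from scans after it.

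The cost is a protocol wording change and some additional event entry over a scan-to-decision interval that the documents do not state. The eCRF is already used for the Heart Team decisions, so participation up to that point needs no new visit. Nothing in the statistical analysis has to change.
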